7.0 QUALITY OF LIFE ASSESSMENT

Measuring quality of life (QOL) outcomes in cancer patients has become an important mandate for clinical trials. It is especially important to assess QOL in phase II cancer clinical trials that are likely to move into the phase III setting. The extent to which treatment impairs QOL is information the patients need when making treatment decisions.

Patients will experience somewhat different symptoms when they receive the different therapies. In order to assess the effects of these treatments, we will assess multidimensional aspects of QOL over the treatment course.

Assessment Schedule

All patients will complete a full assessment battery at baseline, prior to treatment. Patients will then complete an assessment battery every 8 weeks when they come in for their clinical evaluation (see Table 1).

Table 1: Data collection sessions for psychosocial measures

BASELINE	FOLLOW-UP (EVERY 8 WEEKS)

• FACT-G• FKSI-15• Depression (CES-D)	
• FACT-G• FKSI-15• CES-D

Instruments

Several measures used previously in our work on chronic stress and QOL will be used in the proposed study. In all cases, they have proven to be useful and sensitive measures of stress and QOL, have proven to be stable, reliable, and valid with groups of people who are and are not suffering from major depression or other psychiatric disorders.

Quality of Life

The Functional Assessment of Cancer Therapy (FACT) is a cancer-specific measure of health-related quality of life. This instrument was able to discriminate between individuals with metastatic and non-metastatic disease, as well as between patients at different stages of illness. The scale has been found to have good concurrent validity, high internal consistency (0.89), and good test re-test reliability (0.82 to 0.88). The FACT will be completed at each assessment. Kidney cancer specific QOL symptoms will be assessed with the FKSI-15 from the FACT group.

Depression:

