13.0 STATISTICAL CONSIDERATIONS

This is a randomized, two-arm, parallel group, phase II trial enrolling advanced, poor-risk, clear-cell RCC. Patients will be fairly randomized to either temsirolimus (control arm) or pazopanib (experimental arm).

The maximum sample size to be accrued is 90 patients (45 in each treatment arm). The primary measure of efficacy and primary endpoint is progression free survival (PFS). PFS will be monitored on an interim basis and we will use stopping rules for futility to serve as guidelines for early termination. The stopping rules are ad-hoc in nature but are selected in a manner such that the overall type 1 error is controlled at a one-sided 10% with 80% power.

Descriptive and inferential statistics will be used to summarize treatment effects. The mean, standard deviation, median, 25% percentile, 75% percentile, minimum, and maximum will be reported for continuous variables. For discrete variables, descriptive analyses will be based on the distribution of discrete outcomes and will be reported as percentages and patient counts. Time to event endpoints will be descriptively summarized by Kaplan-Meier curves. Point and interval estimates of treatment effect will be based on maximum likelihood methods. For binomially distributed variables, we will report differences in proportions between treatment groups and the 95% confidence interval associated with those differences. We will estimate treatment effects for time to event variables via hazard ratios using Wald scores from Cox proportional hazard regression models. Unless stated otherwise, all statistical tests will be assessed using a two-sided $\alpha = 0.05$ alpha significance level and confidence intervals will be constructed using two-sided 95% and will be based on the normal approximation. Although multiple secondary endpoints will be evaluated we will make no adjustment for multiplicities associated with these multiple tests.

Estimation of Sample Size

The clinical hypothesis we are assessing in this trial is whether patients receiving the experimental therapy have a lower hazard of progression or death relative to patients receiving the control therapy. The statistical hypothesis is stated as:

$$H_0: \log(HR)=0$$

$$H_A: \log(HR)<0$$

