Data Analyses for Quality of Life Measures

Prior to inferential procedures, extensive descriptive analyses will be conducted for each of the measures obtained at each session. Descriptive statistics (e.g., means, ranges, standard deviations) will be computed, together with ninety-five percent confidence intervals for the means. Proportions of subjects falling outside normative ranges for the stress and QOL measures will also be calculated. Values for the standardized scales will be compared to normative data and patients receiving other types of cancer therapy. Graphical methods (e.g., boxplots and histograms) will be employed to more closely examine the distributions of the

measures at each time point. Change scores for the stress and QOL measures will be computed as the simple differences between the baseline measure and subsequent evaluations. Bivariate associations between the raw scores, the change scores, optimism, social support, and demographic variables will be evaluated using Pearson's product moment correlation coefficients together with scatterplots where appropriate. These procedures will allow us to thoroughly characterize the stress and QOL profiles of this patient population across the sessions.

In this study, numerous models will be constructed to analyze the data and, therefore, the results will be treated as hypothesis generating and interpreted with caution. Inferential statistics will comprise paired t-tests of the stress and QOL measures. Significant test results ($p < .05$) will be interpreted as indicating significant changes in depression and QOL associated with the treatment. The association between depression and survival and TTP will also be examined.

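### The quality-of-life plan does not exclude correlating a score with its own change score, and lists optimism and social support, which no instrument in the trial collects

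*Combined protocol and SAP*

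**What the plan says.** Under Data Analyses for Quality of Life Measures, Section 13.0 first defines change: "Change scores for the stress and QOL measures will be computed as the simple differences between the baseline measure and subsequent evaluations". The direction of subtraction is not given. The next sentence plans the correlations: "Bivariate associations between the raw scores, the change scores, optimism, social support, and demographic variables will be evaluated" by Pearson coefficients, with scatterplots where appropriate. It excludes no pair.

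Both sentences belong to a block that the section introduces as descriptive work done before any inference. The inferential tests named afterwards are paired t-tests, with a p < .05 rule. The section adds that its many models are to be treated as hypothesis generating.

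Section 7.0 sets out what is collected. Table 1 lists FACT-G, FKSI-15 and CES-D at baseline and every 8 weeks, and the text agrees: "The FACT will be completed at each assessment"; "Kidney cancer specific QOL symptoms will be assessed with the FKSI-15 from the FACT group"; depression is assessed with the CES-D. For the FACT it reports "good test re-test reliability (0.82 to 0.88". The Section 9.0 calendar has one line for a quality-of-life battery and names no further scale.

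**The concern.** There are two separate faults.

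1. **Coupling.** A change score is built from the baseline and follow-up scores. Measurement error in either one also enters the difference, so a score and its own change are correlated before any treatment effect exists. Read at face value, a negative coefficient for baseline suggests that patients who start badly improve and those who start well decline. Regression to the mean produces that pattern by itself.
2. **Variables with no data.** Optimism and social support are named as analysis variables, but the battery has no instrument or time point for either. Either Section 7.0 omits two instruments or Section 13.0 names variables that the trial does not use. As the documents stand, these correlations cannot be computed.

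What is at stake is how the patient-reported results are described. No decision rule in the trial depends on them.

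**Working it through.** The quality-of-life section states no correlation, power or sample size, so there is no figure of the plan's own to reproduce.

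**Inputs**
- ρ, the correlation of baseline with follow-up when nobody truly changes: 0.82 to 0.88, the FACT test-retest reliability in Section 7.0.
- Assumptions: equal variances at the two times; FACT reliability applied to all three scales, since no test-retest figure is given for FKSI-15 or CES-D.
- ρ of 0.5 to 0.7 as an assumed lower range, to show sensitivity.

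**Formula.** Let X be baseline, Y follow-up and D = Y - X, with common variance σ² and Cov(X,Y) = ρσ².
- Cov(X,D) = ρσ² - σ² = -(1-ρ)σ²
- Var(D) = 2(1-ρ)σ²
- corr(X,D) = -(1-ρ)/√(2(1-ρ)) = -√((1-ρ)/2)
- By symmetry, corr(Y,D) = +√((1-ρ)/2)

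**Numbers**

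| ρ | (1-ρ)/2 | baseline with change | follow-up with change |
|---|---|---|---|
| 0.88 | 0.06 | -0.245 | +0.245 |
| 0.82 | 0.09 | -0.300 | +0.300 |
| 0.70 (assumed) | 0.15 | -0.387 | +0.387 |
| 0.50 (assumed) | 0.25 | -0.500 | +0.500 |

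Subtracting the other way round changes only the signs.

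**Simulation check.** With 40,000 bivariate-normal data sets per case and no true change, the mean baseline-change correlation at ρ = 0.82 was -0.298 with 90 patients and -0.295 with 30. At ρ = 0.88 it was -0.243 and -0.240. The artefact therefore hardly depends on sample size, and more patients would not remove it.

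**What is not affected.** In the same data sets the paired t-test rejected in about 5% of cases, its nominal level.

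**Analysis variables against collected data**

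| Named in Section 13.0 | Collected (Sections 7.0 and 9.0) |
|---|---|
| Quality-of-life scores | FACT-G, FKSI-15 |
| Depression | CES-D |
| Stress | No dedicated scale; Section 7.0 describes its chosen instruments as measures of stress and quality of life |
| Optimism | None |
| Social support | None |

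**The case against.** The strongest defence is that the sentence lists kinds of variable and never says that a score is paired with its own change. Uncoupled pairs, such as change in CES-D with baseline FACT-G, or either with a demographic variable, also fit the text. The correlations are descriptive, and the section asks for caution. All of that is true. But no pair is excluded, so an analyst following the text would compute the coupled ones. A caution about fitting many models guards against chance findings. It does not guard against a coefficient that is non-zero in expectation when nothing has changed.

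Three stronger readings are tempting, and the documents do not support them.

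- A reader might infer that the plan has an inflated false-positive rate here. The general rule in Section 13.0 begins "Unless stated otherwise, all statistical tests will be assessed using a two-sided" and sets alpha at 0.05, but it governs tests, and no test of these correlations is specified. Any rejection rate would describe an analysis that the plan does not contain.
- A reader might infer that the trial will report spurious improvement or decline on each drug. The plan states no such interpretation and does not say that the correlations are run by arm.
- A reader might infer that stress is analysed but never measured. Section 7.0 presents the chosen instruments as measures of stress and quality of life, and Section 13.0 itself moves from stress to depression when it describes the t-tests. The term is loose wording for the collected battery.

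The objection does not reach optimism and social support. Table 1 reads as intact, the text of Section 7.0 matches it, and nothing says that part of another instrument stands in for either variable.

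**Conclusion.** The point holds in a narrow form. As written, the plan admits correlations of a score with its own change. With no real change their expected size is 0.245 to 0.30, negative for baseline and positive for follow-up when change is follow-up minus baseline. This rests on equal variances and on FACT reliability of 0.82 to 0.88 holding for every scale; lower reliability makes the artefact larger. The fault is bias in a descriptive coefficient. Optimism and social support are named for analysis but not collected, and that finding needs no statistical assumption.

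The weight is small. Patient-reported outcomes are a tertiary objective in Section 1.0, the analyses are hypothesis generating, and neither the PFS analysis nor the paired t-tests are touched.

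**What to change.** Amend the quality-of-life part of Section 13.0 before the analysis:

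1. State that a baseline or follow-up score will not be correlated with its own change score.
2. Where a covariate's association with change is of interest, regress the follow-up score on the baseline score plus that covariate. Do not read the baseline slope as real change: with no change and equal variances it equals ρ, here 0.82 to 0.88, which is below 1 through regression to the mean alone. Report the covariate's coefficient as conditional on the observed baseline, because error in that baseline is not removed by adjusting for it.
3. Delete optimism and social support.
4. Replace the references to stress and quality-of-life measures with FACT-G, FKSI-15 and CES-D, and give the direction of subtraction.

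The cost is a wording change. It needs no new data, adds no patient burden and does not affect the sample size.

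### No between-arm comparison of quality of life is specified; the named test is a paired t-test of change, read at p<.05 as change associated with treatment

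*Combined protocol and SAP*

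**What the plan says.** Section 7.0 has all patients complete FACT-G, FKSI-15 and CES-D at baseline and every 8 weeks. It gives the purpose as comparative in spirit: "Patients will experience somewhat different symptoms when they receive the different therapies", and "In order to assess the effects of these treatments, we will assess multidimensional aspects of QOL over the treatment course".

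The analysis is in section 13.0, under Data Analyses for Quality of Life Measures:

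- Change scores: "Change scores for the stress and QOL measures will be computed as the simple differences between the baseline measure and subsequent evaluations".
- External comparators: "Values for the standardized scales will be compared to normative data and patients receiving other types of cancer therapy".
- Inference: "Inferential statistics will comprise paired t-tests of the stress and QOL measures". Results with p<.05 "will be interpreted as indicating significant changes in depression and QOL associated with the treatment".
- A further association: "The association between depression and survival and TTP will also be examined".
- A caveat, placed just before the paired t-tests: "numerous models will be constructed to analyze the data and, therefore, the results will be treated as hypothesis generating and interpreted with caution".

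The section also plans correlations of scores and change scores with optimism, social support and demographic variables. Treatment arm is not a factor in any QOL analysis it describes. Elsewhere in section 13.0 the arms are compared by log-rank test and Cox model for overall survival and by Fisher's exact test for toxicity.

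**The concern.** A paired t-test asks whether the mean change from baseline differs from zero. In poor-risk metastatic disease the mean can move for reasons unrelated to which drug was given, such as the course of the disease or regression to the mean after an unusually poor baseline. The stated reading would credit such a shift to treatment. The other randomised arm experiences the same background shift and is the natural reference, yet the comparators named are normative data and patients on other therapies.

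Two misreadings could follow. A decline common to both arms could be reported as a treatment effect. If the tests are run by arm, significance in one arm only could be taken as a difference between the drugs. Section 7.0 says patients need this information when making treatment decisions, so a misleading summary would matter even though the objective is tertiary.

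**Working it through.** The documents give no QOL effect size, SD or power, so there is no planned figure to reproduce. What follows illustrates how the stated rule behaves.

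**Inputs from the documents.** 45 patients per arm; two-sided 0.05 as the general default; assumed median PFS 3.8 months (temsirolimus) and 6.1 months (pazopanib). All are in section 13.0.

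**Assumptions.** Change scores are normal, with effects in SD units of the change score. Both arms decline equally, so the true arm difference is zero. There is one test per arm on one scale at one visit. Section 13.0 does not say whether tests are per arm or pooled, or which visit is tested, so both versions are shown.

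**Rejection probability.** For n pairs and a decline of d SD, the statistic is noncentral t with n−1 degrees of freedom and noncentrality d√n. Write p for the rejection probability. With p₁ and p₂ for the two arms, at least one arm rejects with probability 1−(1−p₁)(1−p₂), and exactly one with p₁(1−p₂)+p₂(1−p₁).

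*45 pairs per arm, d = 0.3.* p = 0.503. At least one: 1−0.497² = 0.753. Exactly one: 2×0.503×0.497 = 0.50.

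*35 pairs per arm, d = 0.3.* p = 0.407. At least one: 0.648. Exactly one: 0.483.

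*Fewer pairs by week 16.* Assume exponential PFS and that only progression-free patients contribute. Week 16 is about 3.68 months. The progression-free fraction is exp(−ln2×3.68/3.8) = 0.51 for temsirolimus and exp(−ln2×3.68/6.1) = 0.66 for pazopanib. Multiplying by 45 gives about 23 and 30 pairs. At d = 0.3, p₁ = 0.280 and p₂ = 0.355. At least one: 1−0.720×0.645 = 0.54. Exactly one: 0.280×0.645+0.355×0.720 = 0.44.

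*Other effect sizes, 45 pairs per arm.* At least one arm rejects with probability 0.451 at d = 0.2 and 0.936 at d = 0.4.

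*Pooled arms, 90 pairs.* p = 0.80 at d = 0.3, with no arm difference. Pooling can also hide a real difference: if the arms move 0.3 SD in opposite directions (true difference 0.6 SD), simulation with 20,000 runs gives 4% rejection for the pooled paired test and 80% for a two-sample test.

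**Check on the alternative.** When both arms decline by the same 0.4 SD, a two-sample t-test on change scores rejects in 5% of runs, as it should. Its power at 45 per arm is 0.65 for a 0.5 SD difference and 0.80 for 0.6 SD. The difference detectable with 80% power is about (1.960+0.842)×√(2/45) = 0.59 SD.

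**The case against.** The strongest reply is that this is a tertiary objective, that the plan itself calls the results hypothesis generating and urges caution, and that the objective in section 1.0 asks only to determine patient reported outcomes, without naming a comparison. Descriptive statistics with confidence intervals at each session answer part of it. That stands, and it limits the weight of the point. It does not cure it: straight after the caveat, the plan names the test and fixes a reading that the test cannot bear.

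Several stronger readings are tempting and are not supported:

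- *The arms will never be compared on QOL.* Section 13.0 refers in general terms to summarising treatment effects and mentions numerous undescribed models. These leave room for a comparison but do not specify one.
- *The plan claims that changes are caused by treatment.* Its wording is association.
- *The plan will set significance in one arm against non-significance in the other.* Nothing says so; it is a foreseeable misuse.
- *A randomised comparison would remove every bias.* It deals with shared disease course and regression to the mean, but not with selective drop-out. The plan's own PFS assumption implies different attrition by arm.
- *Stress is analysed but not collected.* Section 7.0 describes the chosen instruments as measures of stress as well as QOL, so the phrase can mean the collected battery. Only optimism and social support are clearly absent.

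**Conclusion.** The point holds in this form: the specified QOL inference is a paired test of change from baseline, its stated reading links significant change to treatment, and no between-arm comparison is specified in a randomised trial that wants to learn how the therapies affect QOL. A reader might infer that the patient-reported-outcome objective cannot be met at all. The documents do not support that, because the objective is broad and partly served by description.

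The illustrative rates depend on the assumed decline, normality and, except for the pooled figure, one test per arm. The 45-pair figures also need complete follow-up. The 23 and 30 pairs rest on exponential PFS and on assessments ending at progression, whereas section 5.6 allows some patients to continue first-line treatment beyond it. The qualitative conclusion needs none of these numbers. The primary PFS analysis and the secondary endpoints are untouched. The change is worth making because it is cheap, but it is not critical to the trial's main result.

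**What to change.** In the QOL part of section 13.0:

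1. Make the inferential analysis a pre-specified between-arm comparison for FACT-G, FKSI-15 and CES-D, using first-line (pre-crossover) visits only, since sections 5.4 and 5.6 repeat the assessments after crossover. One suitable choice is a baseline-adjusted repeated-measures model with arm, visit and arm-by-visit. Other pre-specified between-arm contrasts would also serve. Report the pazopanib-minus-temsirolimus difference with its 95% CI.
2. State the missing-data assumption and report the number assessed by arm and visit, because drop-out at progression may differ between arms.
3. Keep within-arm paired changes as descriptive and delete the sentence that reads p<.05 as change associated with treatment.
4. Remove optimism and social support from the analysis text, as the battery does not collect them.

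The cost is some SAP wording and a little more analysis; no new data are needed. The drawback is modest power, about 0.59 SD detectable with 80% power even with all 45 per arm, so the result should be presented as an estimate with its interval and remain hypothesis generating.

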5.5 Off Treatment Follow-up (30 days after stopping therapy)

Attempts will be made to follow-up with the patient in 30 days after the last dose of study drug. If a patient cannot return for the 30-day assessment and contact cannot be made due to disease progression, inability to return, hospice care, death, etc, this will not be considered a protocol deviation. Reporting to the IRB for deaths and other serious adverse events will be performed.

- Record concomitant medications.
- Adverse events will be assessed
- Optional blood draw for correlative studies

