5.6 Crossover Phase

- At progression by RECIST, if they have not suffered an adverse event that would preclude them from continuing with systemic therapy and after the applicable washout period, of 2 weeks, patients who continue to meet the eligibility criteria will begin treatment with the remaining agent.

Note:

- At the discretion of the treating physician, the patient may continue on their 1st-line agent if the treating physician believes the patient is benefitting, despite progression by RECIST.
 - Patient may start their 2nd-line therapy within 2 weeks from the last dose of the agent given in 1st-line, if felt indicated by the treating physician.
 - Patients who develop progressive disease while receiving the 1st-line agent may receive radiation therapy or undergo surgery if indicated and continue to receive treatment on protocol, as long as the 2nd-line agent is commenced within 8 weeks from discontinuation of the 1st-line agent.
- For the cross-over stage of the study, patients will repeat the schedule of assessments as provided in the study calendar and section 5.4. Cardiovascular assessments will only be repeated if more than 24 weeks from the previous exams and only for those who'll be receiving pazopanib. A MRI/CT of the brain will be performed at crossover to rule out any progression before the start of crossover therapy at the discretion of the physician.
 - Screening blood work must have been performed within the past 14 days before starting the new treatment.
 - Optional blood draws will continue the same schedule as indicated in the study calendar.

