5.7 Long-Term Follow-up

Patients will be followed for overall survival every 3 months after removal from final study therapy. Follow-up will consist of a phone call, e-mail correspondence or medical record review.

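### Paired t-tests of quality of life use only patients who still attend, so later-visit decline is likely to be understated when patients leave because they are getting worse

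*Combined protocol and SAP*

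**What the plan says.** Section 7.0 sets the collection schedule for FACT-G, FKSI-15 and CES-D. After the baseline battery, "Patients will then complete an assessment battery every 8 weeks when they come in for their clinical evaluation". In the Section 9.0 calendar the QOL row is marked at screening and every 8 weeks. The optional blood row has a third mark for the off-treatment visit.

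Section 5.5 provides a contact after treatment ends ("Attempts will be made to follow-up with the patient in 30 days after the last dose of study drug") and lists concomitant medications, adverse events and an optional blood draw, but no questionnaire. Section 5.7 follows survival only: "Follow-up will consist of a phone call, e-mail correspondence or medical record review". In crossover (Section 5.6), "patients will repeat the schedule of assessments as provided in the study calendar and section 5.4", so QOL collection continues for patients who go on to the second agent.

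For analysis, Section 13.0 says: "Change scores for the stress and QOL measures will be computed as the simple differences between the baseline measure and subsequent evaluations". It continues: "Inferential statistics will comprise paired t-tests of the stress and QOL measures". Results with p below .05 "will be interpreted as indicating significant changes in depression and QOL associated with the treatment". The same paragraph adds that "the results will be treated as hypothesis generating and interpreted with caution", and Section 1.0 lists patient-reported outcomes as a tertiary objective.

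Nothing states how scores lost to dropout, ill health or death are handled. No repeated-measures model, completion report or sensitivity analysis is named for QOL.

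**The concern.** A change score does not exist for a patient with no score at the later visit, so the paired test omits that patient without comment. The documented routes out of collection are largely routes of ill health: symptomatic deterioration (10.3.3), a toxicity delay of six weeks or more (6.1), intercurrent illness or serious events (12.0), failing the conditions for crossover (5.6), and death. Those who remain at week 16 or 24 are then likely to be fitter than those who began.

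At stake is the description of what treatment does to QOL. Section 7.0 itself says patients need this when choosing treatment, and that it matters most in phase II trials likely to lead to phase III. A decline that is real in the whole group may look small, or go undetected, among those still attending.

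**Working it through.** The plan has no QOL figure to reproduce: it gives no SD, meaningful difference, sample size or expected missingness for these measures. The check has three steps.

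**1. How many scores may be lost.** Inputs: control median OS 10.9 and PFS 3.8 months (Section 2.3), and experimental median PFS 6.1 months (Section 13.0). Assumption: constant hazards, so the share with an event by time t is 1 - 0.5^(t/median). At 4.345 weeks per month, weeks 8, 16 and 24 are 1.84, 3.68 and 5.52 months. Example: dead by week 16 = 1 - 0.5^(3.68/10.9) = 21%.

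| | Week 8 | Week 16 | Week 24 |
|---|---|---|---|
| Dead, control | 11% | 21% | 30% |
| PFS event, control | 29% | 49% | 63% |
| PFS event, pazopanib | 19% | 34% | 47% |

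Progression alone does not end collection, because the schedule repeats in crossover. Loss of scores in the control arm therefore lies roughly between the first two rows. It is not a strict bracket, since a patient can leave for toxicity without progressing.

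**2. What a completer test then reports.** All inputs in this step are assumptions. One arm of 45 has scores at baseline and weeks 8, 16 and 24. The mean change is -2 per visit, so -6 at week 24. Between-patient SD is 13, slope SD 3 per visit and residual SD 6. At each visit 80% of those remaining are retained. Cumulative loss is 1 - 0.8, 1 - 0.8², 1 - 0.8³ = 20%, 36%, 49%, which sits between the death and PFS rows above. The odds of leaving are multiplied by 1 (no link), 1.5 or 2.0 for each 5-point decline.

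Check of the no-link case: the SD of the week-24 change is √((3×3)² + 2×6²) = √153 = 12.4. Completers number 45 × 0.512 = 23, so the SE is 12.4/√23 = 2.6, and -6/2.6 = -2.3. This agrees with the simulated power of about 60%.

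| Leaving depends on | Odds | Completer change | CI coverage | Power | Likelihood model |
|---|---|---|---|---|---|
| Nothing | 1.0 | -6.0 | nominal | 60% | about -6 |
| Last observed change | 1.5 | about -3.8 | 86% | 31% | about -6 |
| Last observed change | 2.0 | about -2.8 | 77% | 20% | about -6 |
| Unseen current score | 1.5 | about -1.9 | – | – | about -3.4 |
| Unseen current score | 2.0 | about 0 | – | – | about -1.8 |

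At 89% retention per visit (89%, 79%, 70% remaining, which matches loss by death alone), with leaving tied to observed change, completers show about -4.8 and -4.1.

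**3. Cross-check by another route.** Suppose only the healthiest fraction f is observed, and health correlates ρ with QOL change. The upward bias in the mean change is ρ·φ(c)/f SD, with c the normal quantile at 1 - f. At week 16:

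- f = 0.79 (loss by death only): φ(c)/f = 0.36, giving 0.11, 0.18 and 0.25 SD for ρ = 0.3, 0.5 and 0.7.
- f = 0.51 (scores end at a control PFS event): φ(c)/f = 0.78, giving 0.23, 0.39 and 0.55 SD.

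With ρ = 0 the bias is zero. Both routes agree on direction. The size depends on a link that the documents do not give.

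**The case against.** **QOL is exploratory.** It is a tertiary objective and the plan calls for caution. This stands and limits the consequence. It does not remove a bias in one direction, and significant results are still to be attributed to treatment.

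**A reader might infer that a non-significant result will be reported as no effect.** The text interprets only significant results and says nothing about null ones.

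**A reader might infer that earlier declines are discarded.** They are not. A patient who worsens at week 8 and then leaves stays in the week-8 summaries and in any week-8 paired test, and is absent only afterwards.

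**A reader might equate PFS events with lost scores, or conclude that the control arm is distorted more.** Crossover repeats the schedule, and Section 5.6 also lets some patients stay on the first agent past progression. PFS is therefore not time to last QOL score, and no between-arm QOL test is named for an imbalance to distort.

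**The calendar is partly broken in the available text.** One of its repeated column headings could be misread as 8-weekly assessment off treatment. The contrast with the blood row and its footnote, and the silence of Section 5.5, support no off-treatment battery.

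**The remedy is not a cure.** The likelihood model recovers -6 only when leaving depends on scores already observed. Deterioration between 8-weekly visits suggests dependence on the unseen score, and then the model is biased too, though less than completers. It also implicitly carries scores past death. A mean among living attenders is a legitimate description if labelled as such. These points stand and shape the fix.

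**Conclusion.** The concern holds in limited form. The stated test is conditional on attendance, collection stops for patients too ill to continue, and nothing handles the missing scores. If leaving is related to worsening QOL, later-visit tests understate decline. In the illustration with leaving tied to observed change, a true -6 appears as about -3.8 or -2.8 at 80% retention, and about half or more of the power is lost. With no such link there is no bias.

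That the results will describe the patients doing best is a likely inference and not a fact in the documents. The effect sizes rest on assumed SDs, retention and odds, and the attrition shares rest on constant hazards and historical control medians. Only the QOL conclusions are affected; the primary PFS analysis is not.

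**What to change.** In Section 13.0, replace the paired t-tests with a likelihood-based repeated-measures model:

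- Terms: arm, visit, arm-by-visit and baseline score, using all available scores, including those of patients who later leave.
- Limit it to a prespecified number of early visits, for example through week 24, so that the covariance can be estimated with 45 per arm.
- Describe the result as an estimate that does not treat death as a score.

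Report by arm and visit the numbers alive, on study and completing the battery, with reasons for missing scores. Give the existing battery at the 30-day off-treatment visit when the patient attends. Add one sensitivity analysis that assigns worse values after departure for deterioration or death.

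The cost is SAP wording, slightly more analysis and one more questionnaire at an existing visit. The 30-day battery will still miss patients who cannot return. The model assumes that departure depends on observed scores; the sensitivity analysis probes that assumption but does not remove it.
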